5 ENROLLMENT AND WITHDRAWAL

5.1 Enrollment

Two hundred (200) prisoners meeting enrollment criteria will be enrolled and stratified according to male/female and sentenced/non-sentenced (e.g. required vs. not required to meet with a probation officer), and randomized to receive XR-NTX before re-entry with follow-up XR-NTX treatment at NET Steps, or randomized to receive their first dose of XR-NTX when they report to NET Steps same day of release up to 30 calendar days post release. Should a prisoner not be released from PPS at the reported release date, and has received his baseline injection of Vivitrol, and the extended incarceration exceeds 30 days, the study will reset his baseline date and administer a 2nd pre-release restart shot prior to the new release date. Additional reset injections may be needed if new release dates are not met. Prisoners will be told that three additional XR-NTX doses will be available at NET Steps and that if they change their mind after reentry they can receive another treatment of their choice. Urine drug tests, adverse events, and a breathalyzer will be done weekly with brief assessments at months 1, 2, 4 and 5, and more detailed assessments at months 3 and 6. PPS data and publicly available criminal justice system information (<http://ujportal.pacourts.us/docketsheets/cp.aspx>) will document rearrests and re-incarcerations. Reasons for screen failure will be recorded; those who relapse will be restarted on XR-NTX or offered the most appropriate treatment at NET Steps or another program of their choice. Efforts will be made to obtain follow-up data on all participants according to the intent to treat design.

5.2 Inclusion criteria:

Opioid dependent with physiological features according to DSM-5; interested in XR-NTX treatment; eligible to have health benefits reinstated; detoxified; age 18 or above; not being transferred to serve a longer sentence in a State or Federal prison; provide their address or phone number along with the names and contact information of

3 or more persons likely to know where they can be reached with permission to contact them if unable to be reached in other ways; able to speak and read English, provide informed consent and correctly answer 9 of 10 study quiz items. Women who are sexually active (except women who are no longer having menstrual cycles or have had both ovaries removed, or have had their uterus removed, or have had tubal ligation) must agree to use one of the following methods of birth control from the date they sign this informed consent until a month after their final dose of study drug:

- a. Hormonal contraception (oral contraceptive, contraceptive implant, or injectable hormonal contraceptive)
- b. Double-barrier birth control (condom plus intrauterine device, diaphragm plus spermicide, etc.)
- c. Maintenance of a monogamous relationship with a male partner who has been surgically sterilized by vasectomy. Participants must also be able to have access to NET Steps via car or public or other transportation after reentry.

5.3 Exclusion criteria:

Planning to move from the Philadelphia area within the next 6 months; being mandated to inpatient substance abuse treatment greater than 30 days; neurological, cardiovascular, renal, hepatic (ALT, AST or GGT >3 times top limit of normal) or another medical disorder that seriously impairs or makes hazardous ability to participate; active tuberculosis; currently psychotic, homicidal, suicidal; uncontrolled seizure disorder; history of allergy to naltrexone, PLG, carboxymethylcellulose, or any other components of the diluent; chronic pain for which opioids are needed; sentenced to naltrexone.

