Candidates who complete all inclusion procedures will be randomized into two groups; group A who will be scheduled to return to the research office prior to re-entry for a drug test, a breathalyzer test, another pregnancy test (females), and naloxone challenge, and group B who will be scheduled to for a drug test and naloxone challenge after release within 7 days at the NET treatment clinic. Those with a opioid positive drug test will be asked to return in 3 days for a repeat test; failure to have an opioid negative test on the second occasion will count as a relapse. Patients who fall into this category will be referred for other treatment or can be restarted on study medication if they are detoxed and elect to continue. These patients will continued to be followed for their weekly and monthly assessments. Those in group A or B with an opioid negative drug test and who pass the naloxone challenge will receive their first dose of XR-NTX with continuing XR-NTX for 3 months thereafter at NET Steps.. A benefits manager will schedule an appointment with the participant after they have met the inclusion criteria, have been randomized, and have a valid release date. Those who change their mind about XR-NTX will be eligible for methadone, buprenorphine-naloxone, intensive outpatient treatment without medication, or referral to another program if they so choose. If a subject in Group A, who received an injection before release from PPS is held over in PPS pass the expected release date by 30 days but not greater than 6 months, the subject will not be given a second injection inside the prison. The subject will be considered in the study but not injected until the new established release date for his next injection. The injection visit dates will be reset to begin as his first injection, with the next injection post release.

If a subject in Group A, who received an injection before release from PPS is held over in PPS more than the expected release date but less than or equal to 30 days from his first injection, the subject’s next injection will be considered his 2nd injection and his visit schedule will not change.

Table 1: Study Interventions and Assessments Flow Chart

	Months 1-3	Month 6
--	-------------------	----------------

XR-NTX Before Reentry (N=100)	XR-NTX + Therapy + Follow Up	Therapy + Follow Up
XR-NTX After Reentry (N = 100)	XR-NTX + Therapy + Follow Up	Therapy + Follow Up

5.6 Randomization Procedures:

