All participants will be offered a psychosocial intervention that focuses on recovery and adherence to treatment and will be delivered in the Re-Entry track at NET Steps by certified addictions counselors in an Intensive Outpatient (IOP) format or an Outpatient Program (OP) track as specified by the PA Client Placement Criteria. The primary modality for IOP is 9 hours/week of group and .25 to .5 hours/week of individual supportive therapy for 3-4 months followed by 3-4 hours of group and individual therapy/week that focuses on reentry into sober, law-abiding society. The OP track is 2.5 hours per month of which 1 hour or all of the 2.5 hours per month can be individual counseling. NET Steps has operated a reentry track for 4 years because staff found that newly released inmates have unique issues and do not mix well with standard IOP patients. The primary treatment component is described in a NIDA monograph (<http://archives.drugabuse.gov/adac/ADAC5.html>) and based on “Living in Balance: Moving from a Life of Addiction to a Life of Recovery,” developed by Hoffman et al. (2003). It consists of 12 Core Topics that provide basic information about addiction and recovery that patients explore using session-specific, reproducible worksheets and is supplemented by 20 sessions that build on the core topics using worksheets supplemented by Gorski’s relapse prevention techniques as described in Technical Assistance Publication series No. 19: “Counselor’s Manual for Relapse Prevention with Chemically Dependent Criminal Offenders” (<http://kap.samhsa.gov/products/manuals/taps/19.htm#top>).

6.8 Pharmacokinetics and Pharmacodynamics: There is a transient peak of naltrexone about two hours after injection followed by a second peak 2-3 days later that reaches approximately 25 ng/ml followed by a decline to about 12 ng/ml to day 7 with a more gradual reduction that reaches 1-2 ng/ml in 30 days. The once/month injection reduces first pass metabolism to 6-beta-naltrexol that occurs after the oral formulation, thus allowing for less total drug to be administered than the oral, though total naltrexone exposure is 3-4 times higher over 28 days than with a 28-day course of the 50 mg/day oral dose.

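### Sections 5.1 and 5.5 give conflicting dosing rules for Group A participants held long past their expected release, so some may leave prison on an expired injection

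*Combined protocol and SAP*

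**What the plan says.** Under section 4.1, both arms are offered the drug, three further doses after the first, counseling and a benefits manager. The planned difference is when the first dose is given: before release in Group A, after release in Group B.

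Two sections deal with a participant who has been injected and is then not released on time.

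- Section 5.1 applies when the extended stay exceeds 30 days. It does not name Group A, but only Group A is injected before release. It says "the study will reset his baseline date and administer a 2nd pre-release restart shot prior to the new release date", and adds: "Additional reset injections may be needed if new release dates are not met". It sets no upper limit on the length of the hold.
- Section 5.5 has two rules for Group A. The first covers anyone "held over in PPS pass the expected release date by 30 days but not greater than 6 months". Its instruction for such a person reads: "the subject will not be given a second injection inside the prison". He stays in the study but is "not injected until the new established release date for his next injection". It continues: "The injection visit dates will be reset to begin as his first injection, with the next injection post release". The second rule is for a participant "held over in PPS more than the expected release date but less than or equal to 30 days from his first injection". His next injection counts as his second and his schedule stands.

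Neither section refers to the other or says which prevails.

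**The concern.** One section orders a dose before release and the other forbids it inside the prison, for the same participant. Staff can follow only one of them.

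The choice matters because dose timing relative to release is what the trial compares. Section 2.2 says that one dose blocks opioid effects for a month. It also cites a study in which drug-related mortality in the first fortnight after leaving prison was 3 to 8 times that of weeks 3 to 12. If 5.5 is followed, a Group A participant can enter that fortnight without the cover that his arm is meant to provide. He would still be analysed in Group A, which is correct, but at release he would resemble Group B.

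**Working it through.** **The plan's own figure.** The power statement in 13.3 uses 100 per arm, 10% attrition by month 3, relapse of 50% against a rate about 20 points lower, and two-sided alpha 0.05. With n = 100 × 0.90 = 90 per arm, Cohen's effect size is |2·arcsin√0.50 − 2·arcsin√0.30| = 1.571 − 1.159 = 0.412. Power = Φ(0.412 × √(90/2) − 1.960) = Φ(0.80) = 0.788, in line with the stated 80%. Dose timing is not an input, so the hold-over rules leave this figure as it is.

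**The rules side by side.** Let d be the days from the pre-release injection to the expected release date, and h the days held past that date. The age of the injection at release is d + h. The documents do not give d; d ≥ 0 because the injection precedes expected release.

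| Rule | Applies when | Action |
|---|---|---|
| 5.1 | extended stay > 30 days; start of count not spelled out; no upper limit | restart injection before the new release date, repeated if that date is missed |
| 5.5, first | h from 30 days to 6 months | no second injection in prison; next one not before the new release date |
| 5.5, second | h > 0 and d + h ≤ 30 | schedule unchanged |

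1. *Conflict.* For h above 30 days and up to 6 months, 5.1 and the first rule of 5.5 both apply. This is so wherever 5.1 starts its count, because h > 30 implies d + h > 30. One requires a pre-release dose; the other bars it in prison.

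2. *Age of the injection at release under 5.5.* d + h ≥ 0 + 30 = 30 days. If no dose follows release at once, it is at least 30 + 14 = 44 days old by the end of the first fortnight. At the upper end it is about 6 months plus d. Section 6.8 describes "a more gradual reduction that reaches 1-2 ng/ml in 30 days". The documents give no level at which blockade fails, so I rely only on the one-month duration in 2.2.

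3. *Gap within 5.5.* The first rule needs h ≥ 30; the second needs d + h ≤ 30. A participant with 30 − d < h < 30 meets neither. Taking d as an assumption:
   - d = 0: no gap
   - d = 7: h of 24 to 29 days (6 values)
   - d = 10: h of 21 to 29 days (9 values)
   - d = 14: h of 17 to 29 days (13 values)

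   For example, with d = 10 and h = 25 the injection is 35 days old but the hold is only 25 days. Section 5.1 catches this participant if its 30 days run from the injection (35 > 30), but not if they run from the release date (25 < 30). The second is the more natural reading.

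4. *Scale.* No hold-over rate is given. Each affected participant is 1/100 = 1% of Group A. Section 5.1 itself expects that new dates may be missed more than once.

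**The case against.** The best defence is that 5.5 should be read as a whole. It may mean no dosing during the hold, then an injection tied to the new release date that counts as the new first injection, with the following one after release. That is close to 5.1, and it narrows the conflict. It does not remove it: 5.5 still excludes an injection inside the prison, and 5.1 requires one before release. A dose given outside on the day of release would be the same as the earliest Group B appointment in 4.1.

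It can also be said that 5.5 is the more specific text, and that prison officials decide procedures inside the prison (14.2.1). That stands as a reason to obtain their agreement. A procedures manual is foreseen in 4.2, and it or the schedule pages may settle the matter; their content is not in the text reviewed. The protocol is still what the IRBs approve, and it should not carry two opposing dosing instructions.

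Two stronger readings are tempting. A reader might infer that held-over participants face a hazard beyond that of the control arm. The documents do not support this: at release they are roughly where Group B is by design, without active blockade and with a dose on offer. A reader might also infer that Group B's first-dose window is contradictory, at 7 days in 4.1 and 5.5 but 30 days in 5.1. The first two concern when the visit is booked and the third when the participant reports. A booking target and an outer limit are compatible, so a label would help but there is no error.

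**Conclusion.** The point holds as an internal conflict with a design consequence, and should be fixed. For Group A participants held 30 days to 6 months past expected release, 5.1 and 5.5 cannot both be followed, and the split clocks in 5.5 leave some shorter holds outside both of its rules. Under 5.5 as written, a participant assigned to dosing before reentry can be released on an injection at least 30 days old. This erodes the arm contrast and removes protection that Group A was meant to have.

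The conclusion rests on a literal reading of 5.5 and on the one-month blockade in 2.2. The textual conflict is certain; the number of participants it touches is not known.

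A reader might infer that the primary result or its power is compromised. The documents do not show that. The intent-to-treat comparison (13.2, 13.5) and the stated power are unchanged, and without a hold-over rate no effect on the estimate can be computed. Nor can drug levels be projected into a date of lost blockade, since no threshold is given.

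**What to change.** Amend 5.5 to agree with 5.1, and use one clock in both sections: days since the last injection.

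- At 30 days or fewer, the schedule stands, as the second rule of 5.5 already provides.
- At more than 30 days, give nothing during the hold, then one restart injection shortly before the new release date, after the usual drug test and naloxone challenge, with baseline reset. If that date is missed, apply the same rule again.
- Say whether the 6-month limit in 5.5 is kept, since 5.1 has none.

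Report for Group A the distribution of days from last pre-release injection to release. Release dates are in Lock & Track (4.3.4). Keep the intent-to-treat analysis as planned. While amending, one sentence could label Group B's 7 days as the appointment target and 30 days as the outer limit, if that is what is meant.

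The cost is a protocol amendment with approval from the Penn and City IRBs (section 18) and agreement from prison officials (14.2.1). Some extra doses will be needed, but 5.1 already foresees them and the drug is supplied free (6.2).

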5.4 Strategies For Recruitment And Retention

The Philadelphia Prison System (PPS; city jail) is an outstanding location to study XR-NTX for the following reasons: (1) All opioid addicted prisoners are detoxified except those that were on a licensed methadone program at the time of incarceration; these patients represent less than 5% of all opioid addicted prisoners. For those on methadone, their dose and the last date they received it are verified and they are continued on methadone via a contract with NET Steps, a nearby program that has treatment staff in the PPS and provides it “behind the walls” via a satellite site, hence “NET@PPS”. At reentry, NET@PPS patients are transitioned to NET Steps or back to their original program. This treatment infrastructure within the PPS will be adapted and used to implement the study proposed here; (2) NET Steps has participated in CTN studies, achieved high recruitment and follow-up rates, and has the capacity to treat study participants; (3) The Medical Director at NET Steps and NET@PPS directed pharmacotherapy studies at the Philadelphia VA before coming to NET Steps where he participated in XR-NTX studies and worked with [name] and other members of the Penn research staff; (4) The Director of the PPS Medical Services is a PhD economist that worked for Blue Cross/Blue Shield before coming to the PPS, is familiar with the health and population burdens of untreated opioid addiction, and is very interested in this study as is the PPS Commissioner and Commissioner of the Philadelphia Department of Behavioral Health. The research team (Penn, NET Steps, and NET@PPS) will organize a Community Advisory Board (CAB) consisting of 10 members, half recovering opioid addicted individuals that have been incarcerated and half members of the local community. The CAB will be led by the two Recovery Specialists mentioned above and meet bi-monthly throughout the study, and be attended by members of the research team who will observe and respond to questions. In addition to leading CAB meetings, the Recovery Specialists will participate in weekly research and treatment staff meetings, provide advice on solving problems that emerge in the course of the study including how to interest and engage prisoners, answer questions about study-related issues, and help locate and schedule participants for follow-up appointments.

The design is summarized below; a detailed description of the measures is provided later.

All admissions to the PPS are medically screened on the first day, including questions about drug use. Screening will help identify study candidates, as will daily interactions between NET@PPS staff and PPS healthcare providers. In addition, [name] and the Director of Social Work Services at PPS have suggested that the PPS can make announcements and hand out study information and sign-up sheets during the initial days of confinement. Additional information could be provided via a brief video on the PPS closed circuit TV system.

5.5 Participant Selection

The study staff distributes study flyers to prisoner representatives at PPS prisoner-staff meetings that occur once a month. These flyers are then posted in each unit. Interested inmates are requested by the flyer to put in a sick call slip to the medical provider who notifies us by secured email of the request. Study staff then goes up to the prison and requests a private visit with the inmate. At this visit, the research staff will provide detailed information about the study and provide the inmate with an opportunity to ask questions. Those continuing to be interested will be asked to review, discuss, and sign the informed consent and take a 10-item quiz testing their understanding of the study. Those who cannot read or answer 9 of 10 quiz questions after 3 retries will be ineligible. Upon signing the consent and passing the quiz screening assessments will be begin. Historical data will be gathered from PDP through the medical database using the PPS contractor. Existing historical data cannot be older than 60 days with the exception of HIV and PPD tests. If the research study performs the HIV tests, then pre-test counseling for the HIV test will be conducted.

Candidates who complete all inclusion procedures will be randomized into two groups; group A who will be scheduled to return to the research office prior to re-entry for a drug test, a breathalyzer test, another pregnancy test (females), and naloxone challenge, and group B who will be scheduled to for a drug test and naloxone challenge after release within 7 days at the NET treatment clinic. Those with a opioid positive drug test will be asked to return in 3 days for a repeat test; failure to have an opioid negative test on the second occasion will count as a relapse. Patients who fall into this category will be referred for other treatment or can be restarted on study medication if they are detoxed and elect to continue. These patients will continued to be followed for their weekly and monthly assessments. Those in group A or B with an opioid negative drug test and who pass the naloxone challenge will receive their first dose of XR-NTX with continuing XR-NTX for 3 months thereafter at NET Steps.. A benefits manager will schedule an appointment with the participant after they have met the inclusion criteria, have been randomized, and have a valid release date. Those who change their mind about XR-NTX will be eligible for methadone, buprenorphine-naloxone, intensive outpatient treatment without medication, or referral to another program if they so choose. If a subject in Group A, who received an injection before release from PPS is held over in PPS pass the expected release date by 30 days but not greater than 6 months, the subject will not be given a second injection inside the prison. The subject will be considered in the study but not injected until the new established release date for his next injection. The injection visit dates will be reset to begin as his first injection, with the next injection post release.

If a subject in Group A, who received an injection before release from PPS is held over in PPS more than the expected release date but less than or equal to 30 days from his first injection, the subject’s next injection will be considered his 2nd injection and his visit schedule will not change.

Table 1: Study Interventions and Assessments Flow Chart

	Months 1-3	Month 6
--	-------------------	----------------

XR-NTX Before Reentry (N=100)	XR-NTX + Therapy + Follow Up	Therapy + Follow Up
XR-NTX After Reentry (N = 100)	XR-NTX + Therapy + Follow Up	Therapy + Follow Up

5.6 Randomization Procedures:

Randomization will be stratified according to male/female and sentenced/not sentenced (e.g. meet/not meet with probation/parole officer. Those who relapse will be referred to the most appropriate alternative at NET Steps or a program of their choice, or offered XR-NTX if they so choose after completing detoxification and the testing procedures described above to make certain they are free of physiologic dependence before receiving XR-NTX. Follow-up assessments will be done every 4 weeks through month 6, as described above. HIV and hepatitis risk reduction counseling is provided at NET Steps as part of ongoing treatment, as is counseling about the possibility of infections, adverse drug reactions, and overdoses from illicit drug use.

